3.2 DISCUSSION OF TRIAL DESIGN, INCLUDING THE CHOICE OF CONTROL GROUP(S)

All patients will receive active treatment as prolonged use of placebo would not be appropriate. The design as open label study with no comparison group is appropriate for assessing the long-term tolerability and safety of nintedanib in pediatric patients with fibrosing ILDs.

This trial will follow the study InPedILD[®] to address EMA's request on the collection of additional safety and efficacy data as discussed during the PIP negotiations.

In addition to patients rolled over from the InPedILD[®] study, in order to address the high unmet medical need for safe and efficacious treatment of this devastating condition, newly identified children and adolescents with clinically significant fibrosing ILD from already participating centres will have the possibility to enter in this trial if they meet the eligibility criteria.

3.3 SELECTION OF TRIAL POPULATION

It is anticipated that at least 30 patients on treatment at the end of the InPedILD[®] trial, from approximately 40 sites in about 21 countries, will consent to participate (and thus receive treatment (if eligible)) in this trial.

In addition, considering enrolment of 2 patients/month across around 40 sites, approximately 20 to 30 newly identified patients are expected to enter treatment in an estimated recruitment period of 18 months with a screen failure rate around 50%. Extension of the study population beyond that of the parent trial is aimed at addressing a high unmet medical need for safe and efficacious therapy for fibrosing ILDs in children and adolescents.

Re-enrolment of screen failed patients will be permitted once. Patients who did not qualify for entering treatment during the early months of the recruitment period might qualify for entering treatment during the late months of the recruitment period of the study. A new informed consent/assent will be signed by the patient/parent(s)/legal guardian and the patient

will be assigned a new unique patient number. The previous patient number will be collected via the electronic Case Report Form (eCRF).

A log of all patients enrolled into the trial (i.e. who have an informed consent signed) will be maintained in the Investigator Site File (ISF) irrespective of whether they have been treated with investigational drug or not.

If retrospectively it is found that a patient has been entered in error (=did not meet all inclusion criteria or met one or more exclusion criteria), the sponsor or delegate should be contacted immediately. Based on an individual benefit-risk assessment by the investigator in discussion with the patient and its parents/legal guardian and discussion with the sponsor, a decision will be made whether continued trial participation is possible or not.

3.3.1 Main diagnosis for trial entry

Main diagnosis for trial entry is identical with that of the parent trial i.e. clinically significant fibrosing ILD as defined by clinical and radiological criteria detailed below.

For patients who rollover from the parent trial InPedILD[®], eligibility of these patients will be established based on a limited number of criteria listed below. Exceptionally, patients that reached adult age during participation of 1199-0337 will be allowed to participate in 1199-0378.

For newly recruited patients, all eligibility criteria based on InPedILD[®] study apply and are listed below.

Please refer to [Section 8.3.1](#) (Source Documents) for the documentation requirements pertaining to the in- and exclusion criteria.

3.3.2 Inclusion criteria

For new patients:

1. Children and adolescents 6 to 17 years old at Visit 2. In France, only adolescents 12 to 17 years old at Visit 2.
2. Signed and dated written informed consent and assent, where applicable, in accordance with ICH-GCP and local legislation prior to admission to the trial.
3. Male or female patients. Female of childbearing potential (WOCBP¹) must confirm that sexual abstinence is standard practice and will be continued until 3 months after last drug intake, or be ready and able to use a highly effective method of birth control per ICH M3 (R2) that results in a low failure rate of less than 1% per year when used consistently and correctly, in combination with one barrier method, from 28 days prior to initiation of study treatment, during treatment and until 3 months after last drug intake. Sexual abstinence is defined as abstinence from any sexual act that may result in pregnancy. A list of contraception methods meeting these criteria is provided in the parental information and in CTP [Section 4.2.2.3](#).

¹ A woman is considered of childbearing potential (WOCBP), i.e. fertile, following menarche and until becoming post-menopausal unless permanently sterile.

Permanent sterilisation methods include hysterectomy, bilateral salpingectomy and bilateral oophorectomy. Tubal ligation is NOT a method of permanent sterilisation.

4. Patients with evidence of fibrosing ILD on HRCT within 12 months of Visit 1 as assessed by the investigator and confirmed by central review.
5. Patients with FVC % predicted $\geq 25\%$ at Visit 2.
[Note: Predicted normal values will be calculated according to GLI (Global Lung Initiative)]
6. Patients with clinically significant disease at Visit 2, as assessed by the investigator based on any of the following:
 - Fan score ≥ 3 , or
 - Documented evidence of clinical progression over time based on either
 - a 5-10% relative decline in FVC% predicted accompanied by worsening symptoms, or
 - a $\geq 10\%$ relative decline in FVC % predicted, or
 - increased fibrosis on HRCT, or
 - other measures of clinical worsening attributed to progressive lung disease (e.g. increased oxygen requirement, decreased diffusion capacity).Instructions on Fan score will be given in [Appendix 10.2](#).

For roll-over patients from the InPedILD[®] study:

Only criteria 2 and 3 listed for new patients are applicable with the following additional inclusion criterion:

7. Patients who completed the InPedILD[®] trial as planned and who did not permanently prematurely discontinue study treatment.

For patients who prematurely discontinued treatment permanently in 1199-0337 but are potentially eligible and for completed patients from parent trial not able to roll over into the extension trial within 12 weeks following their End of Treatment Visit in the parent trial: Inclusion criteria for new patients are applicable except criteria 4, and 6 (as eligibility for these criteria has been confirmed already in 1199-0337 and does not need to be repeated) and also except inclusion criterion 1 for completed patients from parent trial not able to roll over within 12 weeks following their End of Treatment Visit in the parent trial.

3.3.2.1 Evidence of fibrosing ILD for new patients:

Determination of fibrosing ILD on HRCT by the investigator will be based on clinical evaluation. However, given the lack of published guidelines regarding imaging criteria for the diagnosis of fibrosing lung disease in children, central review confirmation to determine eligibility will be based on pre-defined imaging criteria to ensure consistency. The imaging criteria to be used will be determined by expert consensus and included in the imaging manual provided to study sites.

For patients with previous pathological findings of fibrosis on lung biopsy, confirmation of fibrosis on HRCT will be required with at least one of the following imaging findings on one HRCT scan.

Any of the following biopsy findings or diagnoses will be accepted as documentation of fibrosis as confirmed by central review:

- Nonspecific interstitial pneumonia (NSIP), fibrosing
- Usual interstitial pneumonia (UIP)
- Evidence of interstitial fibrosis on a significant* component of the lung biopsy
- Evidence of lobular remodelling on a significant* component of the lung biopsy
- Honeycomb lung

*based on the opinion of the central reviewer.

Confirmation of fibrosis on HRCT will be made if at least one of the following imaging criteria are met within 12 months of screening visit (Visit 1) as confirmed by central review:

- Reticular abnormality or
- Traction bronchiectasis or
- Architectural distortion or
- Honeycombing

Co-existing features cystic abnormalities or ground glass opacity are acceptable but are not counted as features that confirm fibrosis. Co-existing multifocal non-fibrotic, non-dependent consolidations (e.g. organizing pneumonia, infection) will not be allowed.

For patients without any documented lung biopsy or whose biopsy results do not meet the biopsy criteria for fibrosis listed above, confirmation of fibrosis on two HRCT scans will be required.

At least two different findings of the following imaging findings are required on at least two HRCT scans (most recent one must be within 12 months of Visit 1):

- Reticular abnormality,
- Traction bronchiectasis,
- Architectural distortion with/without ground glass opacification,
- Honeycombing,
- Cystic abnormality.

Co-existing ground glass opacity is acceptable but is not counted as feature that confirms fibrosis. Co-existing multifocal non-fibrotic, non-dependent consolidations (e.g. organizing pneumonia, infection) will not be allowed.

3.3.3 Exclusion criteria

For new patients:

1. AST and/or ALT >1.5 x ULN at Visit 1.
2. Bilirubin >1.5 x ULN at Visit 1.
3. Estimated Glomerular Filtration Rate (eGFR) <30 mL/min/1.73m² at Visit 1 (please refer to [Appendix 10.3](#)).

[Note: Laboratory parameters from Visit 1 have to satisfy the laboratory threshold values as shown above. Visit 2 laboratory results will be available only after the visit In case, at Visit 2, the results do no longer satisfy the entry criteria, the Investigator has to

decide whether it is justified that the patient remains on study drug. The justification for decision needs to be documented. Laboratory parameters that are found to be abnormal at Visit 1 are allowed to be re-tested (once) if it is thought to be a measurement error (i.e. there was no abnormal result of this test in the recent history of the patient and there is no related clinical sign) or the result of a temporary and reversible medical condition, once that condition is resolved.]

4. Patients with underlying chronic liver disease (Child Pugh A, B or C hepatic impairment) at Visit 1.
5. Other investigational therapy received within 1 month or 5 half-lives (whichever is shorter but ≥ 1 week) prior to Visit 2 except investigational therapy received in InPedILD[®] trial.
6. Significant pulmonary arterial hypertension (PAH) defined by any of the following:
 - a. Previous clinical or echocardiographic evidence of significant right heart failure
 - b. History of right heart catheterization showing a cardiac index ≤ 2 l/min/m²
 - c. PAH requiring parenteral therapy with epoprostenol/treprostinil
7. In the opinion of the Investigator, other clinically significant pulmonary abnormalities.
8. Cardiovascular diseases, any of the following:
 - a. Severe hypertension, uncontrolled under treatment, within 6 months of Visit 1.
Uncontrolled hypertension is defined as
 - i. In children 6 to ≤ 12 years old: ≥ 95 th percentile + 12 mm Hg or $\geq 140/90$ mm Hg (whichever is lower) (systolic or diastolic blood pressure equal to or greater than the calculated target value) (please refer to [Appendix 10.5](#)). Not applicable in France.
 - ii. In adolescents 13 to 17 years old: systolic blood pressure ≥ 140 mm Hg or diastolic blood pressure ≥ 90 mm Hg (please refer to [Appendix 10.5](#)). In France, applicable for adolescents 12 to 17 years old.
 - b. Myocardial infarction within 6 months of Visit 1
 - c. Unstable cardiac angina within 6 months of Visit 1
9. Bleeding risk, any of the following:
 - a. Known genetic predisposition to bleeding
 - b. Patients who require
 - i. Fibrinolysis, full-dose therapeutic anticoagulation (e.g. vitamin K antagonists, direct thrombin inhibitors, heparin, hirudin)
 - ii. High dose antiplatelet therapy
[Note: Prophylactic low dose heparin or heparin flush as needed for maintenance of an indwelling intravenous device, as well as prophylactic use of antiplatelet therapy are not prohibited.]
 - c. History of haemorrhagic central nervous system (CNS) event within 12 months of Visit 1
 - d. Any of the following within 3 months of Visit 1:
 - i. Haemoptysis or haematuria
 - ii. Active gastro-intestinal (GI) bleeding or GI – ulcers
 - iii. Major injury or surgery (investigator's judgment)
 - e. Any of the following coagulation parameters at Visit 1:
 - i. International normalized ratio (INR) > 2

- ii. Prolongation of prothrombin time (PT) by $>1.5 \times$ ULN
- iii. Prolongation of activated partial thromboplastin time (aPTT) by $>1.5 \times$ ULN
- 10. History of thrombotic event (including stroke and transient ischemic attack) within 12 months of Visit 1.
- 11. Known hypersensitivity to the trial medication or its components (i.e. soya lecithin).
- 12. Patients with documented allergy to peanut or soya.
- 13. Other disease that may interfere with testing procedures or in the judgment of the investigator may interfere with trial participation or may put the patient at risk when participating in this trial.
- 14. Life expectancy for any concomitant disease other than ILD <2.5 years (investigator assessment).
- 15. Female patients who are pregnant, nursing, or who plan to become pregnant while in the trial.
- 16. Patients not able or willing to adhere to trial procedures, including intake of study medication.
- 17. Patients who must or wish to take any drug considered likely to interfere with the safe conduct of the trial according to investigator's benefit-risk assessment for the individual patient
- 18. Patients with any diagnosed growth disorder such as growth hormone deficiency or any genetic disorder that is associated with short stature (e.g. Turner Syndrome, Noonan Syndrome, Russell-Silver Syndrome) and/or treatment with growth hormone therapy within 6 months before Visit 2. Patients with short stature considered by the investigator to be due to glucocorticoid therapy may be included.
- 19. Patients <13.5 kg of weight at Visit 1 (same threshold to be used for male and female patients).

For roll-over patients from the InPedILD[®] study:

Only criteria 11, 12, 13, 15, 16, 17 and 19, listed for new patients are applicable with the following additional exclusion criterion:

- 20. Patient not compliant in parent trial (InPedILD[®]), with trial medication or trial visits, according to investigator's judgement.

Roll-over patients may qualify for participation even though other exclusion criteria may have been met during the participation in InPedILD[®], if the investigator's benefit-risk assessment for the individual patient remains favourable. This should be discussed with sponsor before the roll-over of patient.

For patients who prematurely discontinued treatment permanently in 1199-0337 but are potentially eligible and for completed patients from parent trial not able to roll over into the extension trial within 12 weeks following their End of Treatment Visit in the parent trial:

All exclusion criteria for new patients are applicable. In addition, the following additional exclusion criterion is applicable for patients who prematurely discontinued treatment permanently in 1199-0337:

- 21. Patients who experienced drug-related adverse events during parent trial leading to permanent study treatment discontinuation.

3.3.4 Discontinuation of patients from treatment or assessments

Patients may discontinue trial treatment or patient/parent(s)/legal guardian may withdraw consent/assent to trial participation as a whole (“withdrawal of consent”) with very different implications; please see [Sections 3.3.4.1](#) and [Section 3.3.4.2](#) below.

However, if the patients agree, they should stay in the trial even if continued trial treatment is not possible: roll-over patients should attend further trial visits until Visit 15 and new patients should attend until the overall end of trial to ensure their safety and to collect important trial data.

Measures to control the withdrawal rate include careful patient selection, appropriate explanation of the trial requirements and procedures prior to trial enrolment, as well as the explanation of the consequences of withdrawal.

The decision to discontinue trial treatment or withdraw consent to trial participation and the reason must be documented in the patient files and eCRF. If applicable, consider the requirements for Adverse Event collection reporting (please see [Section 5.2.7.2](#)).

3.3.4.1 Discontinuation of trial treatment

An individual patient will discontinue trial treatment if:

- The patient wants to discontinue trial treatment or if parent(s)/legal guardian want(s) the patient to discontinue trial treatment. They will be asked to explain the reasons but have the right to refuse to answer.
- The patient has repeatedly shown to be non-compliant with important trial procedures and, in the opinion of both the investigator and sponsor representative, the safety of the patient cannot be guaranteed as he / she is not willing or able to adhere to the trial requirements in the future.

In the following cases discontinuation of trial medication is highly recommended. Only in special circumstances the investigator, upon thorough assessment of all available clinical data and taking into consideration the potential risks associated with administration of nintedanib, may decide not to withdraw the trial medication, even though one or more of the below mentioned criteria are fulfilled. In such a case, continuation of treatment with trial medication should be discussed with the patient/parent(s)/legal guardian, and the decision and reasoning documented in the source data.

- Major surgery, including any abdominal or intestinal surgery.
- Anti-coagulation. Patients who require full-dose therapeutic anticoagulation (e.g. vitamin K antagonists, heparin, hirudin, direct thrombin inhibitors, etc.), or high-dose antiplatelet therapy. Prophylactic low dose heparin or heparin flush as needed for maintenance of an indwelling intravenous device, as well as prophylactic use of antiplatelet therapy is allowed.
- Major thrombo-embolic events e.g. stroke, deep vein thrombosis, pulmonary embolism, myocardial infarction.
- Increased risk of bleeding e.g. haemorrhagic CNS event, gross / frank haemoptysis or haematuria, active GI-bleeding or GI-ulcers.

In case of a temporary reason, trial treatment should be restarted if medically justified, please see [Section 4.1.4](#)

In case, the laboratory results at Visit 2 do no longer satisfy the entry criteria, the Investigator has to decide whether it is justified that the patient remains on study drug. The justification for decision needs to be documented in the patient's medical records.

The trial medication has to be permanently discontinued in the following circumstances:

- The patient experiences signs of hepatic injury attributable to trial drug, as defined in [Section 5.2.7.1.4](#).
- In the opinion of the Investigator, the patient experiences unacceptable adverse events despite dose adjustments and supportive care, as defined in [Section 4.1.2](#).
- The patient needs to take concomitant medication that interferes with the safety of the investigational medicinal product or other trial treatment. Please refer to [Sections 4.2.1](#) and [4.2.2](#).

The patient can no longer receive trial treatment for medical reasons such, adverse events, other diseases, or pregnancy.

If a patient becomes pregnant during the trial the investigational product must be interrupted immediately, and the patient will be followed up until birth of the child/children or otherwise termination of the pregnancy. The study medication may be only re-introduced once the child has been born and the mother is no longer nursing, if supported by individual benefit risk as judged by the investigator. The data of the patient will be collected and reported in the clinical trial report (CTR) until patient's last visit, and any events thereafter will be reported in the Boehringer Ingelheim (BI) drug safety database. Refer to [Section 5.2.7.2.3](#) for detailed information on event reporting in case of pregnancy.

In case of permanent discontinuation of trial medication, it is of utmost importance for the robustness and integrity of the trial results that the patient remains in the study and returns to all regularly scheduled visits until the end of the planned observation period. For those patients who are unable to complete the remaining scheduled visits, every attempt will be made to get information on vital status as outlined in the [Flow Chart](#) and [Section 6.2.3](#).

If it is intended by a treatment discontinued patient to use available nintedanib outside the trial after trial treatment discontinuation, the patient should directly undergo to the EoS visit 28 days after the EOT visit (no vital status will be required for this patient).

If new efficacy / safety information becomes available, Boehringer Ingelheim will review the benefit-risk-assessment and, if needed, instruct to pause or discontinue the trial treatment for all patients or take any other appropriate action to guarantee the safety of the trial patients.

[figure not shown]

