4.2.1.2 Management of liver enzyme elevations

Nintedanib can be associated with increased liver enzymes. Concomitant use of other drugs known to cause liver enzyme elevations should be evaluated. For a detailed guidance on how to manage liver enzyme elevations, please refer to [Table 4.2.1.2: 1](#) for patients.

Table 4.2.1.2: 1 Recommendations for managing liver enzyme elevations

	AST or ALT increase to			Signs of hepatic injury*
	>1.5x to <3x ULN	≥3x to <5x ULN and no signs of hepatic injury	≥5x to <8x ULN and no signs of hepatic injury	
At Visit 2 for new patients (start of treatment)	Permanently discontinue trial medication or justify continuation ¹	Permanently discontinue trial medication	Permanently discontinue trial medication	Permanently discontinue trial medication
At any other Visit for new patients and At all visits for roll-over patients	Continue as planned ²	Reduce dose or interrupt trial medication ³	Interrupt trial medication	Interrupt trial medication (may subsequently need to be permanently discontinued ⁵)
		Close observation ⁴ After 2 weeks or any time later	Close observation ⁴ After 2 weeks or any time later	CLINICAL EVALUATION OF HEPATIC-INJURY
	<3x ULN	≥3x ULN	<3x ULN	≥3x ULN
	Reduced: return to initial dose. Interrupted: restart at reduced dose. Monitor every 2 weeks for at least 8 weeks	Permanently discontinue trial medication Close observation ⁴	Restart at reduced dose Monitor weekly for 4 weeks, then every 2 weeks for at least 8 weeks	Permanently discontinue trial medication. Close observation ⁴

Footnotes:

*Signs of hepatic injury are defined as

- ALT and/or AST ≥ 8 fold ULN
- ALT and/or AST ≥ 3 fold ULN and total bilirubin ≥ 2 fold ULN
- ALT and/or AST ≥ 3 fold ULN and unexplained INR >1.5
- ALT and/or AST ≥ 3 fold ULN and unexplained eosinophilia ($>5\%$)
- ALT and/or AST ≥ 3 fold ULN and appearance of fatigue, nausea, vomiting, right upper abdominal quadrant pain or tenderness, fever and/or rash

¹Investigator to confirm in writing that continuation is justified (e.g. intermittent fluctuation of transaminases).

²According to visit schedule. Consider additional control visits as adequate.

³To be decided by Investigator, based on individual risk assessment.

⁴Close observation: Re-test ALT and AST, alkaline phosphatase, total bilirubin, and eosinophils within 48 to 72 hours, then approximately 7 days, then approximately 2 weeks, preferably by using appropriate visit lab kit as instructed to site by the sponsor.

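### New patients with AST/ALT ≥3x ULN at Visit 2: the liver table says stop permanently, while Sections 3.3.3 and 3.3.4.1 leave the choice to the investigator

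*Protocol*

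**What the plan says.** New patients are excluded if AST or ALT exceeds 1.5x ULN at Visit 1 (Section 3.3.3, criterion 1). Safety bloods are drawn again at Visit 2, but "Visit 2 laboratory results will be available only after the visit", and the first dose is taken during that visit (Section 4.1.4).

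Two places then govern an abnormal Visit 2 result.

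- **Sections 3.3.3 and 3.3.4.1.** The note under exclusion criteria 1 to 3 begins "In case, at Visit 2, the results do no longer satisfy the entry criteria" and hands the matter to the investigator. Section 3.3.4.1 repeats it: "the Investigator has to decide whether it is justified that the patient remains on study drug". Both ask for a documented justification.
- **Section 4.2.1.2.** Table 4.2.1.2:1, titled "Recommendations for managing liver enzyme elevations", has a dedicated row beginning "At Visit 2 for new patients (start of treatment". In the >1.5x to <3x ULN column the entry is "Permanently discontinue trial medication or justify continuation", with a footnote requiring written confirmation. In the other three columns (≥3x to <5x ULN, ≥5x to <8x ULN, signs of hepatic injury) the entry is permanent discontinuation with no alternative.

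Section 3.3.4.1 also lists circumstances in which the drug must be stopped permanently. The liver item reads "The patient experiences signs of hepatic injury attributable to trial drug", with the definition taken from Section 5.2.7.1.4.

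**The concern.** A child who qualified at Visit 1, was dosed at Visit 2 and then proves to have had an ALT of 4x ULN falls under two instructions. The table recommends stopping for good. Sections 3.3.3 and 3.3.4.1 let the investigator write a justification and continue at any level.

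The route through the protocol favours the looser text. For liver elevations Section 5.2.3 cites Section 4.1.2 for monitoring and Section 3.3.4 for withdrawal. Section 4.1.2 is about dose selection and has no liver thresholds; Section 3.3.4 contains the open-ended discretion.

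What is at stake is patient safety. A drug that Section 4.2.2.1 says is associated with rises in liver enzymes and bilirubin could be continued at a level where the sponsor's own table recommends stopping. No estimate or test depends on this.

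**Working it through.** No figure in the plan needs reproducing. The check is to set the two sources side by side for a new patient at Visit 2.

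| AST/ALT at Visit 2 | Table 4.2.1.2:1, Visit 2 row | Sections 3.3.3 and 3.3.4.1 | Agree? |
|---|---|---|---|
| >1.5x to <3x ULN | Stop, or justify in writing | Investigator decides and documents | Yes |
| ≥3x to <5x ULN, no injury signs | Stop permanently | Investigator decides and documents | No |
| ≥5x to <8x ULN, no injury signs | Stop permanently | Investigator decides and documents | No |
| Signs of hepatic injury (including ≥8x ULN) | Stop permanently | Mandatory stop if attributable to trial drug; otherwise investigator decides | In part |

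**Does the mandatory stop close the gap?** Under Section 5.2.7.1.4, transaminases alone count as hepatic injury only from 8x ULN. Between 3x and 8x they count only together with raised bilirubin, INR or eosinophils, or with symptoms. Isolated values of ≥3x to <8x ULN are therefore outside it. In the fourth column the attribution condition is awkward too: Section 6.2.2 lists the Visit 2 blood draw before the first dose, so an abnormality in that sample could hardly be attributed to the drug. That column does have another safeguard. Signs of hepatic injury trigger the DILI checklist (Section 5.2.7.1.4) and AESI reporting within 24 hours (Section 5.2.7.2.2), neither conditional on attribution. The residual gap is therefore mainly the two middle columns, 2 of 4.

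**Does the stricter Visit 2 row look deliberate?** At other visits the table offers dose reduction or interruption at ≥3x to <5x ULN and interruption at ≥5x to <8x ULN. At Visit 2 both become permanent discontinuation. That reads as an intended limit, and the other sections do not carry it.

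**How many patients?** Sections 3.3 and 7.5 expect 20 to 30 newly identified patients. Parent-trial patients handled as new add an unstated number. One affected patient among the newly identified would be:

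- 1/30 = 3.3%
- 1/20 = 5.0%

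The documents give no rate of Visit 2 values ≥3x ULN after ≤1.5x ULN at Visit 1, so no expected count can be given.

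**How soon is the next fixed test?** Visit 3 is Day 15 ±3, that is Day 12 to Day 18. Counted from Day 1:

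- 12 − 1 = 11 days
- 18 − 1 = 17 days

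Before then, Section 5.2.3 requires close monitoring and allows more frequent sampling, and intermediate visits are at the investigator's discretion (Section 6.2.2). Footnote 4 of the table sets a firm schedule ("Re-test ALT and AST, alkaline phosphatase, total bilirubin, and eosinophils within 48 to 72 hours, then approximately 7 days, then approximately 2 weeks"), but as the table reads in the text available here it is attached to the other-visits row. Little weight should rest on where a footnote sits in a merged-cell table.

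**The case against.** The best answer is that this is a missing cross-reference and the rules do not compete. Section 3.3.4.1 does not authorise continuation; it requires a decision. An investigator who stops at ≥3x ULN complies with both texts. The table is specific to liver enzymes in new patients at Visit 2, and a specific rule normally prevails over a general one. The log for Global Amendment 1 describes the Section 3.3.4.1 paragraph as a clarification added to match the Section 3.3.3 note, and the same amendment revised the liver table, so nothing suggests an intention to relax the table. The liver guidance is also signposted in the hepatic rows of Table 1.4.2:1 and at the end of Section 4.2.1.

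That reading is reasonable and may well be what the sponsor intends. But no text states the precedence, the table is framed as recommendations, and none of the signposts is attached to the two discretion paragraphs. An investigator who continued at 4x ULN with a written justification would also be complying with Section 3.3.4.1.

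Two further points stand. First, the situation is rare: it needs a rise from ≤1.5x to ≥3x ULN during screening, and the Visit 1 tests are repeated if the interval exceeds 6 weeks. Second, it may affect nobody from now on. Recruitment was estimated at 18 months (Section 3.3), and Global Amendment 1, dated 5 August 2022, already describes the trial as started. Eighteen months from that date is February 2024, before Version 6.0 of 27 November 2024. This is inference; the documents do not say whether entry is closed.

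**Conclusion.** The concern holds as a minor patient-safety inconsistency plus a wrong cross-reference in Section 5.2.3. The misdirection to Section 4.1.2 is an error whichever text is meant to prevail.

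The exposure is small and cannot be turned into an expected number of cases. A patient who was continued would still be monitored, though the extra testing is not on a fixed schedule. The conclusion assumes that the table's column entries read as laid out here and that no site document outside the protocol sets the precedence. If new-patient entry has closed, no further patient is affected. The descriptive analysis of treatment-emergent adverse events does not change.

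**What to change.** 1. In the Section 3.3.3 note and the Section 3.3.4.1 paragraph, add: *For AST/ALT and signs of hepatic injury at Visit 2, follow the Visit 2 row of Table 4.2.1.2:1; continuation may be justified only at >1.5x to <3x ULN.* Leave the investigator's discretion for the other Visit 2 laboratory criteria, such as bilirubin and eGFR, as written.
2. In Section 5.2.3, change the monitoring reference from Section 4.1.2 to Section 4.2.1.2 (Table 4.2.1.2:1), and cite the table beside Section 3.3.4 for withdrawal.

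The drafting cost is two sentences, one corrected reference and one added reference. The thresholds are the sponsor's own, and no assessment, data collection or analysis changes. The sentence does make a recommendation binding at ≥3x ULN, so the sponsor should confirm that this is intended. Amendments need ethics and competent-authority approval (Section 8.1) in approximately 23 countries, so the sensible vehicle is the next amendment made for other reasons. If entry has closed, only the Section 5.2.3 correction still has practical use.
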